5.2 Secondary Outcome Analysis

All secondary outcomes will be analyzed as for a superiority designed trial. Two-sided 95% CIs for

the treatment differences in these outcomes between two groups will be calculated and reported. Secondary outcome analyses will be based on the ITT population unless specified.

5.2.1 Analysis of binary outcomes

Repeated measured binary outcomes will be analyzed with the same tactics as that used for the primary outcome.

Non-repeated measured binary outcomes, referring to need for additional treatment or not, will be summarized by number (%) of participants by treatment group. The proportion difference will be tested by χ^2 methods or fisher exact test. If necessary for analysis, OR with their two-sided 95% CIs of the two groups will be derived from logistic regression. RR and 95% CI were also estimated using a binomial regression with log link function.

5.2.2 Analysis of continuous outcomes

The continuous outcome will be summarized using number of subjects (n), mean, standard deviation (SD), minimum, and maximum by intervention group. The repeated measured outcomes (including changes in z score of LMCA; changes in z score of LAD; changes in z score of LCX; changes in z score of the proximal segment of RCA; changes in z score of the middle segment of RCA) will be analyzed by generalized linear mixed model (GLMM) with intervention, visit and interaction between treatment with visit as fixed effect, patient ID as random effect, their baseline value as covariate variable. The outcomes which are not repeated measures (including change in serum C-reactive protein (CRP) concentration from admission to 72 hours after completion of initial IVIG infusion) will be analyzed by GLM. Gaussian distribution and identity link function will be used in the model. Difference in mean changes of outcome with their two-sided 95% confidence intervals between two groups will be estimated.

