2.2.2 Secondary Outcomes

- 1) Changes in z score of LMCA from admission. Data will be measured at six time points of illness: enrollment, 2th week (± 2 days), 1th month (± 5 days), 3th month (± 5 days), 6th month (± 5 days) and 12th month (± 5 days), respectively.

(Time Frame: from admission to 12 months of illness) (Type: repeatedly measured continuous

variable)

2) Changes in z score of LAD from enrollment. Data will be measured at six time points of illness: enrollment, 2th week (± 2 days), 1th month (± 5 days), 3th month (± 5 days), 6th month (± 5 days) and 12th month (± 5 days), respectively.
(Time Frame: from admission to 12 months of illness) (Type: repeatedly measured continuous variable)

3) Changes in z score of LCX from enrollment. Data will be measured at six time points of illness: enrollment, 2th week (± 2 days), 1th month (± 5 days), 3th month (± 5 days), 6th month (± 5 days) and 12th month (± 5 days), respectively.
(Time Frame: from admission to 12 months of illness) (Type: repeatedly measured continuous variable)

4) Changes in z score of the proximal segment of RCA from enrollment. Data will be measured at six time points of illness: enrollment, 2th week (± 2 days), 1th month (± 5 days), 3th month (± 5 days), 6th month (± 5 days) and 12th month (± 5 days), respectively.
(Time Frame: from admission to 12 months of illness) (Type: repeatedly measured continuous variable)

5) Changes in z score of the middle segment of RCA from enrollment. Data will be measured at six time points of illness: enrollment, 2th week (± 2 days), 1th month (± 5 days), 3th month (± 5 days), 6th month (± 5 days) and 12th month (± 5 days), respectively.
(Time Frame: from admission to 12 months of illness) (Type: repeatedly measured continuous variable)

6) Need for additional treatment or not. The acute KD patients in both arms resistant to the initial IVIG therapy will be given additional treatment, which will be determined by the prescription record.
(Time Frame: at one month of illness) (Type: binary variable)

7) Duration (hours) of fever (defined as an axillary temperature <37.5 for more than 24 hours) after initiation of initial IVIG among participates of two arms.
(Time Frame: from initiation of initial IVIG infusion to the first record of being afebrile) (Type: time-to-event variable)

8) Change in serum C-reactive protein (CRP) concentration from admission to 72 hours after

completion of initial IVIG infusion.

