5.1. Primary Outcome Analysis

5.1.1 ITT analysis of the primary outcome - the primary analysis

The primary analysis will be based on the ITT population as defined above. The primary outcome is a binary outcome: CAL occurs or not within 1 month of illness onset. Since CAL will be repeatedly examined at enrollment, 2 weeks, 1 month, 3 months, 6 months and 12 months respectively, generalized estimating equation (GEE) model will be performed, with treatment, visit and interaction between treatment with visit as fixed effect, patient ID as cluster effect, the mean of 5 coronary artery baseline z scores (described in section 2.2.1) as covariate variable. Risk difference (RD) and two-sided 95% confidence intervals (CI) between the two treatment groups will be estimated from the model using a binomial distribution and identity link function. OR with 95% CI at each time point will be obtained using GEE model with binomial distribution and logit link function. Binomial distribution and log link function will be used to obtain estimation of risk ratio (RR) and 95% CI. Exchangeable correlation structure is assumed for within-group variation for all the GEE models. The P value for the interaction term will be used to determine the statistical significance of the group difference at specific time point.

If the above GEE model does not converge, a poisson distribution will be used for the family function. A negative binomial distribution will be subsequently used for family function in case the GEE model based on poisson distribution does not converge. RD, OR and RR with their 95% CI

estimates will be reported by using identity, logit and log link function, respectively. In the final analysis, a normal family distribution was used because none of the three prespecified distribution models converged. RD and 95% CI estimates were derived using identity link function.

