5.3 Handling of Missing data

Missing baseline covariates will be imputed using simple imputation methods in the covariate adjusted analysis based on the covariate distributions, should the missing values for a particular covariate be less than 5%. For a continuous variable, missing values will be imputed from random values from a permuted normal distribution with mean and SD calculated from the available sample. For a categorical variable, missing values will be imputed from random values from a uniform distribution with probabilities P1, P2, ..., and Pk from the sample. The seed to be used is 20230605. We do not assume the condition that missing of covariate variable at baseline will be over 5%.

6. General Considerations for Data Analyses

SAS (version 9.4) will be used to perform all data analyses and generate majority of data displays. STATA® (version 16.0) or R may also be used for some data analyses and generating statistical graphs. All analyses for the primary and secondary outcome variables will be primarily based on ITT population. Two-side tests and P values will be reported. Regression models for repeated measurement will be used for outcomes that are repeatedly measured, group differences at the prespecified timepoint will be computed and reported.

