6.2 Graphical Displays

Table 1. Baseline characteristics of patients

Analysis Set: ITT population

Variable	Statistic	Treatment A (N=)	Treatment B (N=)	All (N=)
Gender, n (%)	Female			
	Male			
Age (years)	n			
	Mean (SD)			
	Median (IQR)			
	Min-Max			
Height (cm)	n			
	Mean (SD)			
	Median (IQR)			
	Min-Max			
Weight (kg)	n			
	Mean (SD)			
	Median (IQR)			
	Min-Max			
LMCA	n			
	Mean (SD)			
	Median (IQR)			
	Min-Max			
LAD	n			
	Mean (SD)			
	Median (IQR)			
	Min-Max			
LCX	n			
	Mean (SD)			
	Median (IQR)			

Variable	Statistic	Treatment A (N=)	Treatment B (N=)	All (N=)
	Min-Max			
RCA (prox)	n			
	Mean (SD)			
	Median (IQR)			
	Min-Max			
RCA (mid)	n			
	Mean (SD)			
	Median (IQR)			
	Min-Max			

Table 2. Summary for primary outcomes by generalized estimating equation model
Analysis Set: ITT population

		Participants, No. (%)		Generalized estimating equation model analysis		
Primary outcome	Visit	Treatment A	Treatment B	Risk difference (95% CI)	Odds Ratio (95% CI)	Risk ratio (95% CI)
Covariate unadjusted ^a						
CAL	1 month					
	3 months					
	6 months					
	12 months					
Covariate adjusted ^b						
CAL	1 month					
	3 months					
	6 months					
	12 months					

^aThe GEE model only includes the mean of 5 coronary artery baseline z scores as covariate.

^bThe GEE model was adjusted by including ...as covariates.

Table 3. Subgroup analysis of primary outcome by generalized estimating equation model

Analysis Set: ITT population

			Participants, No. (%)		Generalized estimating equation model analysis		
Primary outcome	Variable	Visit	Treatment A	Treatment B	Risk difference (95%CI)	Odds ratio (95%CI)	Risk ratio (95%CI)
CAL	Age (<=1 year)	1 month					
		3 months					
		6 months					
		12 months					
	Age (>1 year)	1 month					
		3 months					
		6 months					
		12 months					
	Gender (F)	1 month					
		3 months					
		6 months					
		12 months					
	Gender (M)	1 month					
		3 months					
		6 months					
		12 months					
	BMI (I)	1 month					
		3 months					
		6 months					
		12 months					
	BMI (N)	1 month					
		3 months					
		6 months					
		12 months					
	BMI (H)	1 month					
		3 months					
		6 months					

			Participants, No. (%)		Generalized estimating equation model analysis		
Primary outcome	Variable	Visit	Treatment A	Treatment B	Risk difference (95%CI)	Odds ratio (95%CI)	Risk ratio (95%CI)
		12 months					

Table 4. Secondary analysis by generalized estimating equation model
Analysis Set: ITT population

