		n, mean (SD)		Generalized estimating equation model analysis	
Secondary outcome	Visit	Treatment A (N=)	Treatment B (N=)	Risk difference (95% CI)	P value
LMCA	1 month				
	3 months				
	6 months				
	12 months				
LAD	1 month				
	3 months				
	6 months				
	12 months				
LCX	1 month				
	3 months				
	6 months				
	12 months				
RCA (prox)	1 month				
	3 months				
	6 months				
	12 months				
RCA (mid)	1 month				
	3 months				
	6 months				
	12 months				

Additional tables will be generated if more analyses are conducted.

7. Study Variable List

Table 1 Variable list

Note: T, text variable; D, The date type; N, Continuous variable; B, binary variable; C, categorical variable

No	Variable	Variable Type	Variable interpretation
1	center	T	Name of center
2	id_center	T	Number of center
3	name_pat	T	Acronym of subject
4	patid	N	Study ID of subject
5	time_start	D	Date of enrollment
6	time_end	D	Date of end
7	investigator		Investigator signature
8	inc_1	B	Meeting the diagnostic criteria of Kawasaki disease
9	inc_2	B	Age ≥ 1 month and weight ≤ 30 kg
10	inc_3	B	Fever ≤ 10 days
11	inc_4	B	All coronary z values are <10 before IVIG administration
12	inc_5	B	Able to complete follow-up
13	inc_6	B	The guardian is fully informed and signs the informed consent
14	exclusion_1	B	Use of hormones or other immunosuppressants 1 month before KD onset
15	exclusion_2	B	Recurrence of KD

16	exclusion_3	B	Body temperature is normal at the time of inclusion ($T \leq 37.5 \geq 24h$)
17	exclusion_4	B	With the following infections: sepsis, septic meningitis, peritonitis, bacterial pneumonia, varicella, and influenza
18	exclusion_5	B	History of serious immune diseases, such as immunodeficiency, or chromosomal abnormalities
19	eligibility	B	Eligibility or not
20	arm	T	Intervention allocation
21	gender	B	Gender
22	birth	D	Date of birth
23	tel	T	Telephone
24	height	N	Height at baseline
25	weight	N	Body weight at baseline
26	id_hospital	T	Hospital admission number
27	date_fisrt_fever	D	Date of first fever
28	date_ivig_on	D	Start date of IVIG administration
29	hour_ivig_on	N	Start time of IVIG administration
30	manifes_fever	B	Clinical feature - fever
31	manifes_fever_days	N	Clinical feature - febrile days
32	manifes_fever_high	N	Clinical feature - maximum heating temperature
33	manifes_conjestion	B	Clinical feature - conjunctivitis
34	manifes_rash	B	Clinical feature - rash
35	manifes_tongue	B	Clinical feature - oral changes
36	manifes_swollen_hand	B	Clinical feature - extremity changes

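### The z-score mixed model states only a patient random effect and one baseline slope, so its visit-by-visit confidence intervals can be miscalibrated; Table 4 names a different model and an effect measure that does not apply

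*SAP*

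**What the plan says.** Secondary outcomes 1 to 5 in SAP section 2.2.2 are the z-score changes of the LMCA, LAD, LCX and the proximal and middle RCA. The first reads "Changes in z score of LMCA from admission. Data will be measured at six time points of illness". There are therefore five post-baseline visits: 2 weeks and 1, 3, 6 and 12 months.

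Section 5.2.2 gives these outcomes a generalized linear mixed model with intervention, visit, "interaction between treatment with visit as fixed effect, patient ID as random effect, their baseline value as covariate variable". It adds that "Gaussian distribution and identity link function will be used in the model" and that "Difference in mean changes of outcome with their two-sided 95% confidence intervals between two groups will be estimated". Section 6 says of repeatedly measured outcomes that "group differences at the prespecified timepoint will be computed and reported".

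The shell for the same five outcomes in section 6.2 is headed "Table 4. Secondary analysis by generalized estimating equation model". Its effect column is labelled "Risk difference (95% CI", next to columns for n, mean and SD.

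Section 5.1.1 does state a correlation structure, but for the GEE models: "Exchangeable correlation structure is assumed for within-group variation for all the GEE models". Section 5.2.2 has no matching statement for the mixed model. Section 5.2.4 sends the exploratory absolute diameters to the same section 5.2.2 method.

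**The concern.** There are two linked problems.

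**The model.** A Gaussian model whose only within-patient term is a patient random effect assumes, by default, the same variance at every visit, the same correlation between any two visits, and the same dependence of change on baseline from 2 weeks to 12 months. That would matter little for one averaged effect. Here each visit gets its own difference, interval and P value, and a standard error pooled over visits is right for a given visit only if that visit has average spread.

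**The table.** Section 5.2.2 and Table 4 name different methods and different effect measures for the same five secondary outcomes. If spread varies by visit, the choice between the two methods changes the interval and P value at each visit.

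**Working it through.** **Plan's own figure.** The SAP gives no SD, correlation or power for any z-score outcome, so there is nothing to reproduce here. Its one design figure (section 3.5) concerns the primary outcome and does not bear on this point.

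**Formula.** Take complete data on the five post-baseline visits, a patient random intercept and one residual variance. The model variance at every visit is then proportional to the mean of the visit-specific residual variances. At visit j:

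- model SE / true SE = r_j = sqrt(mean variance / variance_j)
- type I error = 2 × [1 − Φ(1.96 × r_j)]; coverage = 1 − type I error

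Both standard errors scale with sample size in the same way, so r_j does not depend on n.

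**Case 1: assumed residual SDs 1.28, 1.21, 1.07, 1.01, 0.94.** The variances are 1.6384, 1.4641, 1.1449, 1.0201 and 0.8836. Their sum is 6.1511 and their mean 1.2302.

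| Visit | r_j | Type I error |
|---|---|---|
| 2 weeks | sqrt(1.2302/1.6384) = 0.87 | 8.9% |
| 1 month | sqrt(1.2302/1.4641) = 0.92 | 7.2% |
| 3 months | sqrt(1.2302/1.1449) = 1.04 | 4.2% |
| 6 months | sqrt(1.2302/1.0201) = 1.10 | 3.1% |
| 12 months | sqrt(1.2302/0.8836) = 1.18 | 2.1% |

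**Case 2: SD falling linearly over the five visits, by ratio of first to last.**

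| SD ratio | Coverage, first visit | Coverage, last visit |
|---|---|---|
| 1.0 | 95.0% | 95.0% |
| 1.1 | 93.9% | 96.1% |
| 1.25 | 92.3% | 97.3% |
| 1.5 | 90.1% | 98.7% |
| 2.0 | 86.9% | 99.7% |

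For the last row the variances are 4, 3.0625, 2.25, 1.5625 and 1, with mean 2.375. So r = sqrt(2.375/4) = 0.77 at the first visit and sqrt(2.375/1) = 1.54 at the last.

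**Case 3: the direction can reverse.** For an SD rising linearly from 0.8 to 1.1, type I error is 1.9% at 2 weeks and 8.9% at 12 months.

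**Simulation of the section 5.2.2 model.** Assumptions: 150 per arm, five visits, no treatment effect, correlation between visits decaying from 0.75 (AR(1)), and SDs and baseline correlations as listed.

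| Setting | Coverage, first visit | Coverage, last visit |
|---|---|---|
| Equal SD, equal baseline correlation | 95.7% | 96.1% |
| Equal SD, baseline correlation 0.8 to 0.4 | 98.7% | 90.2% |
| SD 1.6 to 1.0, correlation 0.6 | 87.8% | 97.9% |
| SD 2.0 to 1.0, correlation 0.6 | 83.6% | 99.3% |
| SD 1.6 to 1.0, correlation 0.8 to 0.4 | 93.2% | 94.8% |

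The mean estimated effect stayed within 0.004 of zero throughout, so the issue is interval width and not bias. In the first row all visits lay between 94.6% and 96.1% although the correlation decayed. With complete data it is therefore unequal residual variance that matters, including the part created by a baseline slope that changes over visits.

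**The remedy under the same assumptions.** With a separate variance and baseline slope at each visit, coverage was 94.6% to 95.7% at every visit in the four settings with unequal SD or unequal baseline correlation.

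**The two named methods on the same data.** Both were fitted to the case 1 SDs with 400 patients and 200 runs. Point estimates were identical. The mixed model gave a standard error of 0.111 at every visit. The exchangeable GEE with robust standard errors gave 0.127 at 2 weeks and 0.093 at 12 months, against empirical values of 0.127 and 0.092.

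**The case against.** A reader might infer that the intervals are simply wrong, because coronary dilation in the acute phase later regresses and equal variance therefore cannot hold. The documents do not support this. They give no z-score SD, correlation or trajectory. A change in the mean over time is already absorbed by the visit and treatment-by-visit terms and does not establish a change in variance. With constant residual variance the intervals are correct, and when SD and baseline correlation fell together the two effects nearly cancelled (93.2% and 94.8%).

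It is also fair to say that a single residual variance is the default reading of a silent text. Section 5.2.2 excludes neither a residual structure nor robust standard errors. If the GEE of Table 4 were what is run, with its usual robust variance, the problem would largely disappear. The largest error in case 1 falls at 2 weeks, for which Table 4 has no row. A random-intercept model with a baseline covariate is also a common choice.

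On the table, the column of means and SDs makes it unlikely that anyone would compute a risk difference, so that label is a drafting error.

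What remains: the covariance is left open where it governs the reported intervals, and the text and the shell name two methods that give different standard errors when spread varies. Knowing that one of them would be robust does not say which will be run.

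**Conclusion.** The point holds in conditional form. Section 5.2.2 leaves the per-visit intervals dependent on an unstated assumption of equal residual variance. If spread changes over visits, the intervals are too narrow where spread is above average and too wide elsewhere. In case 1 type I error ranges from 8.9% to 2.1%; for a linear two-fold fall in SD, coverage ranges from 86.9% to 99.7%. All SDs and correlations are assumptions, the data are taken as complete, and missing visits were not examined. Neither the actual size nor the direction can be read from the SAP.

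The contradiction between section 5.2.2 and Table 4 needs no assumption: mixed model against GEE, and difference in mean change against risk difference.

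The point concerns secondary outcomes 1 to 5 and, through section 5.2.4, the exploratory diameters. It does not touch the primary outcome. It should be corrected, but it does not show that any reported estimate is biased.

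**What to change.** In section 5.2.2, specify a repeated-measures model on the post-baseline visits with unstructured within-patient covariance and with treatment-by-visit and baseline-by-visit terms. If the random-intercept model is kept, state that empirical (robust) standard errors are used.

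The SAP records analyses already run and others added during manuscript revision. If z-score results have already been produced, keep the prespecified model and report the new one beside it as a labelled sensitivity analysis, so that the change is not a silent post-hoc replacement.

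Retitle Table 4 to the model actually used and label its effect column *Difference in mean change (95% CI)*. Apply the same specification to the absolute diameters in section 5.2.4.

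The cost is small: a sentence, a table title, a column label and one covariance statement in the program. Five visits need 5 × 6 / 2 = 15 covariance parameters, against 3200 planned children, or 3200 × 0.9 = 2880 after the assumed dropout.

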5.1.2.2 Covariate adjusted analysis of the primary outcome

An analysis of the primary endpoint will be adjusted for baseline information including age, body mass index (BMI), gender and complete or incomplete KD (following the KD diagnostic criteria from the American Heart Association released in 2017). From the above model, the adjusted estimates of RD and two-sided 95% CIs will be derived. The OR and RR with their 95% CIs will also be estimated from the GEE model using logit and log link function as described in Section 5.1.1.

Given the GEE model in the primary analysis has converged, if the GEE model doesn't converge when all covariates are introduced into the model simultaneously, the adjusted model will be established by removing a covariate one by one until the model converges.

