5.2.4 Analysis of other secondary outcomes (Exploratory Outcome Analysis)

The post-hoc secondary outcomes were analyzed using the same statistical methods described above unless otherwise specified. Specifically, these exploratory outcomes included: occurrence of medium-to-giant CAAs among all participants (Section 5.2.1, repeated measured binary outcomes); CAL progression among all participants (Section 5.2.1, non-repeated measured binary outcomes); and changes in absolute diameters of LMCA, LAD, LCX, the proximal and middle segments of RCA (Section 5.2.2, repeated measured continuous outcomes).

Considering the low incidence of large/giant CAAs (<1%), between-group RRs and two-sided 95% CIs were estimated from a GLM with a negative binomial distribution and log link, adjusting for the mean baseline z scores. Participants with large/giant aneurysms at baseline were excluded from this analysis.

For analysis of CAL progression in participants with baseline CAL, the model was further adjusted for age, sex, KD type, baseline sodium level, CRP concentration, and white blood cell count. RR and corresponding 95% CI were estimated.

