72	b2_neutro6d	N	Neutrophil counts at 6 days after IVIG administration
73	b2_neutro9d	N	Neutrophil counts at 9 days after IVIG administration
74	b3_platelet0	N	Blood platelet before IVIG administration
75	b3_platelet3d	N	Blood platelet at 72 hours after IVIG administration
76	b3_platelet6d	N	Blood platelet at 6 days after IVIG administration
77	b3_platelet9d	N	Blood platelet at 9 days after IVIG administration
78	b4_hemoglob10	N	Hemoglobin before IVIG administration - 1
79	b4_hemoglob20	N	Hemoglobin before IVIG administration - 2
80	b4_hemoglob13d	N	Hemoglobin at 72 hours after IVIG administration - 1
81	b4_hemoglob23d	N	Hemoglobin at 72 hours after IVIG administration - 2
82	b4_hemoglob16d	N	Hemoglobin at 6 days after IVIG administration - 1
83	b4_hemoglob26d	N	Hemoglobin at 6 days after IVIG administration - 2
84	b4_hemoglob19d	N	Hemoglobin at 9 days after IVIG administration - 1

85	b4_hemoglob29d	N	Hemoglobin at 9 days after IVIG administration - 2
86	b4_hemoglobunit	T	Unit of hemoglobin
87	b5_hct0	N	HCT before IVIG administration
88	b5_hct3d	N	HCT at 72 hours after IVIG administration
89	b5_hct6d	N	HCT at 6 days after IVIG administration
90	b5_hct9d	N	HCT at 9 days after IVIG administration
91	b6_crp10	N	CRP before IVIG administration - 1
92	b6_crp20	N	CRP before IVIG administration - 2
93	b6_crp13d	N	CRP at 72 hours after IVIG administration - 1
94	b6_crp23d	N	CRP at 72 hours after IVIG administration - 2
95	b6_crp16d	N	CRP at 6 days after IVIG administration - 1
96	b6_crp26d	N	CRP at 6 days after IVIG administration - 2
97	b6_crp19d	N	CRP at 9 days after IVIG administration - 1
98	b6_crp29d	N	CRP at 9 days after IVIG administration - 2
99	b6_crpunit	T	Unit of CRP
100	b7_saa0	N	Serum amyloid A before IVIG administration
101	b7_saa3d	N	Serum amyloid A at 72 hours after IVIG administration
102	b7_saa6d	N	Serum amyloid A at 6 days after IVIG administration
103	b7_saa9d	N	Serum amyloid A at 9 days after IVIG administration
104	c1_esr0	N	Erythrocyte sedimentation rate (ESR) before IVIG administration
105	c1_esr4	N	Erythrocyte sedimentation rate (ESR) after

			IVIG administration
106	c2_alb0	N	Albumin before IVIG administration
107	c2_alb4	N	Albumin after IVIG administration
108	c3_prealb10	N	Prealbumin before IVIG administration - 1
109	c3_prealb14	N	Prealbumin after IVIG administration - 1
110	c3_prealb20	N	Prealbumin before IVIG administration - 2
111	c3_prealb24	N	Prealbumin after IVIG administration - 2

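### The GLM for change in CRP has no stated baseline CRP term, although the repeated continuous outcomes are baseline-adjusted and pre-IVIG CRP is collected; read as written, it gives up precision on one secondary outcome.

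*SAP*

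**What the plan says.** SAP section 2.2.2 defines the eighth secondary outcome as "Change in serum C-reactive protein (CRP) concentration from admission to 72 hours after" the end of the first IVIG infusion, measured once as a continuous variable.

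Section 5.2.2 splits the continuous outcomes into two groups.

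- **Repeated outcomes (five coronary z-score changes).** These go to a mixed model with treatment, visit and their interaction, and with "patient ID as random effect, their baseline value as covariate variable".
- **The single non-repeated outcome (CRP change).** The text is "concentration from admission to 72 hours after completion of initial IVIG infusion) will be analyzed by GLM", and the sentence after it adds only the Gaussian distribution and identity link. No covariate is named.

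Section 5.2.4 sends the exploratory changes in absolute diameter, including the "segments of RCA (Section 5.2.2, repeated measured continuous outcomes", to the same baseline-adjusted repeated-measures model. Fever duration is a time-to-event outcome. CRP change is therefore the only continuous outcome without a stated baseline term.

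The variable list in section 7 contains both measurements that are needed: "CRP before IVIG administration - 1" and "CRP at 72 hours after IVIG administration - 1".

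**The concern.** The difference between two measurements keeps variation from the first one unless the model removes it. Baseline CRP cannot be affected by the randomised treatment, so including it removes that variation without introducing bias. Leaving it out has two consequences:

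- The confidence interval for the treatment difference is wider than the same data allow.
- If the arms differ by chance in pre-treatment CRP, part of that difference stays in the estimated effect. The arm that starts higher tends to show the larger fall.

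There is also a specification problem. An analyst who follows section 5.2.2 literally fits treatment alone. Another, who carries the baseline rule over from the preceding sentence, fits treatment and baseline CRP. They would report different estimates and intervals for the same outcome.

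**Working it through.** **1. The plan's own figure.** The SAP has no design figure for CRP. Its only sample-size statement (section 3.5) concerns the primary outcome: 12.4% against 9.1%, alpha 0.05, power 0.8, 1400 per arm. The usual two-proportion formula with pooled variance, two-sided, gives

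(1.960*sqrt(2*0.1075*0.8925) + 0.842*sqrt(0.124*0.876 + 0.091*0.909))^2 / 0.033^2 = 1382 per arm.

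The stated figure reproduces to within 3% and has no bearing on the CRP model.

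**2. Does another section supply the term?**

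- The covariate-adjusted analysis in section 5.1.2.2 is "adjusted for baseline information including age, body mass index (BMI), gender and complete or incomplete KD"; CRP is not among these.
- Section 5.1.3 carries the primary outcome's strategy over to sensitivity analyses of secondary outcomes, but adds no covariate.
- Baseline CRP appears as a covariate only in section 5.2.4, in the model for progression of coronary lesions among participants who had them at baseline.

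So no section puts baseline CRP into the CRP model.

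**3. Variance with and without the term.** Let s0 and s1 be the SDs of CRP at baseline and 72 hours, rho their correlation, and assume a linear model with a common slope. Per patient:

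- unadjusted change: V_u = s0^2 + s1^2 - 2*rho*s0*s1
- adjusted for baseline: V_a = s1^2*(1 - rho^2)
- difference: V_u - V_a = s0^2 - 2*rho*s0*s1 + rho^2*s1^2 = (s0 - rho*s1)^2

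The difference is never negative, and is zero only if rho*s1 = s0. The direction therefore needs no assumed CRP values.

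**4. Size.** The SAP gives no SD or correlation for CRP, so these are assumptions. Put s0 = 1 and s1 = k.

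| k | rho | V_u | V_a | V_u / V_a | adjusted CI width / planned width |
|---|---|---|---|---|---|
| 1 | 0.2 | 1.60 | 0.96 | 1.67 | 0.77 |
| 1 | 0.4 | 1.20 | 0.84 | 1.43 | 0.84 |
| 1 | 0.6 | 0.80 | 0.64 | 1.25 | 0.89 |
| 0.5 | 0.2 | 1.05 | 0.240 | 4.38 | 0.48 |
| 0.5 | 0.4 | 0.85 | 0.210 | 4.05 | 0.50 |
| 0.5 | 0.6 | 0.65 | 0.160 | 4.06 | 0.50 |
| 0.3 | 0.2 | 0.97 | 0.0864 | 11.2 | 0.30 |
| 0.3 | 0.4 | 0.85 | 0.0756 | 11.2 | 0.30 |
| 0.3 | 0.6 | 0.73 | 0.0576 | 12.7 | 0.28 |

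The last column is sqrt(V_a / V_u). A simulation with 1400 per arm at k = 0.5 and rho = 0.3 gave standard errors of 0.0374 unadjusted and 0.0186 adjusted. That is a ratio of 2.01, against 2.04 by formula.

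**5. Chance imbalance.** If the arms differ by d in mean baseline CRP, the unadjusted contrast is shifted, relative to the adjusted one, by (1 - rho*s1/s0) of d. Over the grid this fraction runs from 1 - 0.6*1 = 0.40 to 1 - 0.2*0.3 = 0.94.

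**The case against.** **Silence is not a decision.** The CRP sentence gives the model class, distribution and link, and does not even list treatment as a term. Section 5.1.2.10 says outright that its GLM is unadjusted; section 5.2.2 does not. This stands in part. A reader might infer that the SAP rules baseline adjustment out, and the text does not support that: the term is omitted, not excluded. The same argument cuts the other way, because the SAP names its adjustment where it wants one, including for a GLM in section 5.2.4. On either reading the model needs one more phrase.

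**The large ratios rest on unsupported inputs.** This stands. A reader might infer that CRP falls so sharply that its change is mostly baseline variation. The documents give no CRP means, SDs or correlation, and a fall in the mean would not by itself fix the ratio of the SDs.

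**The mechanism is easily overstated.** This also stands. The change score need not carry the whole baseline variance: at k = 1 and rho = 0.6 its variance is 0.80*s0^2. A baseline imbalance passes through in full, relative to the adjusted estimate, only if rho = 0.

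**The practical effect is limited.** With 1400 per arm and complete CRP data, the unadjusted 95% half-width is 1.96*sqrt(2*V_u/1400). Over the grid this is 0.06 to 0.09 baseline SDs, which is already narrow. This bears on how much the point matters, not on whether it is correct.

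**Conclusion.** The point holds as a matter of efficiency. As written, section 5.2.2 compares CRP change without baseline CRP, and adding that covariate gives a more precise estimate unless rho*s1 = s0. The direction follows from algebra under a linear model with a common slope; one degree of freedom is negligible at this sample size.

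The size does not follow from the documents. Even the mildest case in the table means 25% more variance than necessary, while the larger ratios apply only if the 72-hour SD is well below the baseline SD.

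A reader might go further and call the CRP comparison biased or invalid. The SAP does not support that: allocation is randomised, so the unadjusted contrast is unbiased on average. One laboratory outcome, the eighth of nine secondary outcomes, is affected. The primary outcome, its sample size and the safety analyses are not.

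**What to change.** In section 5.2.2, state that the GLM for CRP contains treatment and baseline CRP. The outcome definition in section 2.2.2 can stay: with baseline CRP in the model, the change and the 72-hour value give the same treatment estimate.

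The cost is one covariate in one model. No new data are needed. No participant is lost either, because a change in CRP can be computed only for those who have a baseline value.

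Section 5.1.1 already reports a modelling choice made in the final analysis, and section 5.1.2 lists analyses added during manuscript preparation and revision. If the CRP comparison has already been run without the covariate, keep that result and report the adjusted one beside it, labelled as added later.
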